## **10.4 Responsibilities**

## Principal Investigator (PI)

- 1. Checking for ARs when participants attend for treatment.
- 2. Using medical judgement in assigning seriousness and expectedness using the relevant SMPC used locally.
- Ensuring that all SARs, (including RUSAEs) are recorded and reported to the CTRU within 24 hours of becoming aware of the event and provide further follow-up information as soon as available. Ensuring that SARs (including RUSAEs) are chased with CTRU if a record of receipt is not received within 2 working days of initial reporting.
- 4. Ensuring that ARs are recorded and reported to the CTRU in line with the requirements of the protocol.

# Chief Investigator / delegate or independent clinical reviewer

- 1. Clinical oversight of the safety of patients participating in the trial, including an ongoing review of the risk / benefit.
- 2. Using medical judgement in assigning seriousness and expectedness of SARs where it has not been possible to obtain local medical assessment.
- 3. Immediate review of all RUSAEs within 24 hours.

4. Review of specific SARs in accordance with the trial risk assessment and protocol as detailed in the Trial Monitoring Plan.

# CTRU

- 1. Central data collection and verification of ARs, SARs and RUSAEs, according to the trial protocol onto a MACRO database.
- 2. Reporting safety information to the Chief Investigator, delegate or independent clinical reviewer for the ongoing assessment of the risk / benefit according to the Trial Monitoring Plan.
- 3. Reporting safety information to the independent oversight committees identified for the trial (Data Monitoring & Ethics Committee (DMEC) and Trial Steering Committee (TSC)) according to the Trial Monitoring Plan.
- 4. Expedited reporting of RUSAEs, to the REC and Sponsor within 1 working day of CTRU awareness.
- 5. Notifying Investigators of all RUSAEs that occur within the trial which compromise participant safety.
- 6. Preparing annual safety reports for the REC.

# **Trial Management Group (TMG)**

In accordance with the Trial Terms of Reference, the Trial Management Groun (TMG) will provide clinical and practical advice on trial related matters. The TMG is accountable to the TSC and DMEC and are responsible to escalate concerns to these committees.

#### Trial Steering Committee (TSC)

In accordance with the Trial Terms of Reference for the TSC, periodically reviewing blinded safety data and liaising with the DMEC regarding safety issues.

# Data Monitoring & Ethics Committee (DMEC)

In accordance with the Trial Terms of Reference for the DMEC, periodically reviewing unblinded overall safety data to determine patterns and trends of events, or to identify safety issues, which would not be apparent on an individual case basis.

# 11 Endpoints

# 11.1 Primary endpoint

## **Neurocognitive function**

Neurocognitive function (NCF) for the primary endpoint will be measured and assessed using the composite score of the EORTC core CTB COMP; consisting of HVLT-R, TMT-A/B and COWA. Neurocognitive assessments will be performed face-to-face on paper-based tests at baseline and 1, 12, 24, 36, 48 and 60 months post end of RT.

# 11.2 Secondary endpoints

## Additional tests of neurocognitive function

The CNS Vital Signs test battery will be performed at baseline, and 1, 12, 24, 36, 48 and 60 months post-RT. CNS vital sign tests to be assessment include: Verbal Memory (VBM), Visual Memory (VIM), Finger Tapping (FTT), Symbol Digit Coding (SDC), Stroop Test (ST), Shifting Attention (SAT), Continuous Performance (CPT), Perception of Emotion (POET), On-Veral Reasoning (NVRT), and the 4-part Continuous Performance (FPCPT).

Participants will complete this after face-to-face testing for the primary NCF endpoints, on a desktop computer or PC with a mouse, supervised by a research nurse or other qualified individual.

## Health Related Quality of Life (HRQoL)

Health related quality of life questionnaires to be completed by participants at baseline, during the final week of RT and 1, 3, 6, 12, 24, 36, 48, 60 months post-RT. These include the EORTC Quality of life questionnaire core 30 (QLQ-C30), QLQ-BN20, the EQ-5D-5L, MFI questionnaire and the HADS.

#### Endocrinopathy

Endocrine dysfunction will be assessed using blood tests. Dynamic/static testing will be performed for GH/IGF-1, FSH/LH/ testosterone (males) & SHBG (males)/ oestradiol (females), cortisol, T4/T3/TSH, and prolactin. These will be performed at baseline and 6, 12, 24, 36, 48 and 60 months post-RT, as per standard of care.

#### **Treatment compliance**

Data on the treatment participants receive will be collected weekly during radiotherapy. Information will be recorded on the total dose of radiotherapy received (dose and fractions), the overall treatment time (i.e. time between start and end date), details of any interruptions to the radiotherapy and the reasons for these interruptions (i.e. toxicity or other). In the case of PBT, any fractions that are given as photon treatment instead of PBT (e.g. the result of PBT machine breakdown) will also be recorded.

Adherence to the radiotherapy schedule will be defined as a participant that has completed their scheduled course of radiotherapy with no more than two treatment days of interruptions due to toxicity or any other reason.

The number of chemotherapy cycles and doses delivered will also be recorded, along with details of any modifications (delays, dose reductions, omissions) to treatment and their associated reasons.

#### Work & economic impact

WPAI general health (WPAI:GH) will be completed by the participant and their primary caregivers at baseline, during the final week of RT and 1, 3, 6, 12, 24, 36, 48 and 60 months

post-RT. The questionnaire includes six questions about employment, time off and productivity at work and during regular activities, assessing the impact due to overall health and symptoms.

An additional health resource use questionnaire will collect patients' utilisation of health services related to their brain cancer including: NHS and primary health services, hospital based secondary care services and personal costs incurred. Personal costs incurred for caregivers will also be collected. The health recourse utilisation will be collected at baseline and annual follow-up.

#### **Caregiver distress**

The 30-item Caregiver Needs Screen will be completed by the participant's primary caregiver at baseline, during the final week of RT and 1, 3, 6, 12, 24, 36, 48, 60 months post-RT. The questionnaire includes subscales for neurologic and oncologic symptoms, personal communication, communication with healthcare providers, resources and caregiver health.

#### Early and late toxicity

The acute toxicity period has been defined from start of RT to the 3 months post end of RT follow-up assessment. Clinician assessment of acute toxicities will take place on each week of treatment during clinic and during the 1 and 3 month follow-up assessments. The late toxicity period will be defined as after 3 months until the final follow-up visit at 60 months. Clinician assessment of late toxicity will take place during each of the follow-up visits and will be recorded at 6, 12, 24,36,48 and 60 months post start of radiotherapy treatment. Toxicities will also be recorded at each chemotherapy assessment.

All radiotherapy and chemotherapy toxicities will be evaluated using the CTCAE criteria (V5.0) and include all ARs, SARs and RUSAEs.

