#### 8.2.2 Chemotherapy treatment schedule

Chemotherapy should start between 4 and 8 weeks after RT completion.

Chemotherapy is scheduled at 6-weekly intervals (+ 1-week for unavoidable delays, bank holidays etc.) for a maximum of 6 cycles (depending on tolerability) or until disease progression, whichever is sooner. Patients should be treated according to this schedule, as per standard practice.

It is recommended that initial doses (in the absence of renal or hepatic impairment) will be:

**Lomustine** 100mg/m^2, with dose banding/ capping as per the institution's usual practice day 1, PO, on a 42 day cycle, for up to 6 cycles.

**Procarbazine** 100mg/m^2, with dose banding/ capping as per the institution's usual practice once daily on days 1-10 or days 2-11, PO, on a 42 day cycle, for up to 6 cycles.

**Vincristine** 1.4-1.5mg/m^2 (or flat dose of 2mg if this is usual institutional practice), with dose banding/ capping as per the institution's usual practice IV, day 1, on a 42 day cycle for up to 6 cycles. If a patient has a body surface area (BSA) of <1.45m^2, then dosing must be based on BSA.

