#### Early and late toxicity

Summary statistics of safety data on ARs/SARs/RUSAEs experienced will be presented overall and by treatment arm for the acute and late toxicity period. The number and proportion of participants experiencing each CTCAE grade of acute and late toxicities will be summarised.

The long-term collection of clinician recorded toxicities will capture a level of symptom burden as a result of treatment. CTCAE grades of patients over time will be assessed to explore the time dependence of ARs in a population that can often experience chronic conditions. Additionally, this longitudinal data will be explored in relation to other endpoints over time e.g. HRQoL.

Safety monitoring of reactions to chemotherapy will be included and as such will be reported under the toxicity secondary objective, however, there is no hypothesis of expected differences and no plan for formal comparisons – this is being used to inform the safety of

the radiotherapy comparison. These events are collected for monitoring purposes, and completeness of symptom reporting for this patient population across the course of the trial.

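### Late toxicity is defined by calendar time alone, so reactions to most PCV cycles are tabulated as late toxicity and dilute the descriptive comparison of late radiotherapy effects

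*Protocol*

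**What the plan says.** Protocol section 11.2 (Early and late toxicity) sets the two periods by time. For the first: "The acute toxicity period has been defined from start of RT to the 3 months post end of RT follow-up assessment". For the second: "The late toxicity period will be defined as after 3 months until the final follow-up visit at 60 months". It adds that "Toxicities will also be recorded at each chemotherapy assessment", and on content: "All radiotherapy and chemotherapy toxicities will be evaluated using the CTCAE criteria (V5.0) and include all ARs, SARs and RUSAEs".

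Section 13.5, under the same heading, carries these periods into the analysis: "The number and proportion of participants experiencing each CTCAE grade of acute and late toxicities will be summarised". The summaries are by arm and by period. Neither section limits the late period to reactions attributed to radiotherapy.

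On timing, section 8.2.2 says "Chemotherapy should start between 4 and 8 weeks after RT completion", then six-weekly, with one week allowed for unavoidable delay, "for a maximum of 6 cycles (depending on tolerability) or until disease progression, whichever is sooner". Section 13.2 brings acute and late toxicities up to 2 years into the 2-year interim analysis.

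Two other places bear on the point. Section 10.2 gives radiotherapy-related and chemotherapy-related reactions different collection periods. Sections 10.1.4 and 13.5 say that chemotherapy reactions are collected for monitoring, with no expected difference and no formal comparison.

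On visit dates, section 11.2 has late toxicity "recorded at 6, 12, 24,36,48 and 60 months post start of radiotherapy treatment". Section 9.7 and Table 3 count the same visits from the end of radiotherapy.

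**The concern.** Late toxicity in a radiotherapy trial normally means late radiation damage, and Appendix B lists late radiotherapy effects in that sense, as those arising more than 90 days after completion. The section 11.2 definition does not match that meaning, because most of the chemotherapy is given after the boundary. A cycle-4 vomiting episode or neutropenia is an acute drug reaction, yet under the text it is a late toxicity.

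Section 1.3 places the main potential benefit of PBT in normal tissue damage and long-term toxicity. PCV is given in both arms and the protocol expects no difference in its reactions. Adding them to both arms leaves the direction of a late radiotherapy difference intact but makes it look smaller. The 2-year summary is the most exposed, because it accompanies an analysis that may support an early change of practice and has few visits after PCV has finished.

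**Working it through.** The protocol states no toxicity rate, so there is no figure to reproduce. The check is calendar arithmetic on the protocol's own schedule.

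**Inputs.** Boundary: 3 months after the end of radiotherapy (11.2) = 3 × 30.4375 / 7 = 13.0 weeks. PCV start s = 4 or 8 weeks after radiotherapy; interval 6 weeks, up to 6 cycles (8.2.2). Chemotherapy-related reactions are collected to 42 days after the last cycle (10.2), so PCV is taken to end 6 weeks after cycle 6 starts.

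**Cycle starts**, s + 6(k − 1) weeks after radiotherapy:
- s = 4: weeks 4, 10, 16, 22, 28, 34. Cycles 3-6 (4 of 6) start after week 13; PCV ends at week 40.
- s = 8: weeks 8, 14, 20, 26, 32, 38. Cycles 2-6 (5 of 6) start after week 13; PCV ends at week 44.

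Section 9.7 allows ±4 weeks on the visit. If the boundary is the actual visit date, the cycles after it range from 2-6 to 4-6.

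**PCV time in the late period.** 40 − 13 = 27 weeks to 44 − 13 = 31 weeks.
- Of the 36 weeks of PCV: 27/36 = 75% to 31/36 = 86%.
- Of the 3-24 month window, 21 × 30.4375 / 7 = 91.3 weeks: 27/91.3 = 30% to 31/91.3 = 34%.
- Of the 3-60 month window, 57 × 30.4375 / 7 = 247.8 weeks: 27/247.8 = 11% to 31/247.8 = 13%.

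If every cycle takes the one-week allowance, PCV ends at weeks 45-49, and the last share rises to 32/247.8 = 13% to 36/247.8 = 15%.

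**Visits.** Of the late visits (6, 12, 24, 36, 48 and 60 months) only month 6, at about week 26, falls within scheduled PCV. Up to 2 years, the late assessments are months 6, 12 and 24 plus the reviews before 4 or 5 cycles, and only months 12 and 24 come after scheduled PCV.

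**Mechanism.** Suppose a share p_c (photon) or p_t (PBT) of participants has a late radiotherapy reaction of a given grade, and a share b in each arm independently has a PCV reaction of that grade after the boundary. The pooled late proportion is 1 − (1 − p)(1 − b), so the difference between arms becomes (p_c − p_t)(1 − b). With assumed rates of 30% v 15% (not from the protocol), b = 20%, 40% and 60% gives 44% v 32%, 58% v 49% and 72% v 66%. The 15-point difference becomes 12, 9 and 6 points. This shows the direction only. It applies when participants are counted by grade across all reactions; in a table by individual reaction, only terms common to both treatments are mixed. Appendix B lists fatigue and hair loss for both.

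**Start versus end of radiotherapy.** 30 or 33 weekday fractions take 30/5 = 6 or 33/5 = 6.6 weeks. The two readings of the visit date therefore differ by more than the ±4-week window.

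**The case against.** The strongest reply is that there is no toxicity comparison here to damage. Section 13.5 plans descriptive summaries only, with no test and no power. That stands. A reader might infer that PCV reactions swamp the radiotherapy comparison, or that the trial loses power for late toxicity. The documents support neither: they give no reaction rates and plan no such test, and PCV in both arms dilutes rather than biases the comparison unless exposure to it differs by arm.

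Much of the rest limits the size of the problem. PCV occupies a small part of the 5-year window, and five of the six late visits come after it. Section 13.5 also plans to look at grades over time. Neurocognitive and endocrine harms, two of the main very late effects in Appendix B, have their own endpoints. Showing all treatment-related reactions is defensible in an open-label trial, since attribution is made with knowledge of the arm.

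The argument that the split by cause belongs in the statistical analysis plan stands only in part. Table layouts can be left there, but the protocol itself fixes the late period and what it contains, and does not connect either to the separation in section 10.2. An analysis plan restricted to radiotherapy-related reactions would depart from section 11.2 as written.

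**Conclusion.** The point holds as a minor one on a secondary endpoint. As written, reactions from 4 or 5 of the 6 PCV cycles are tabulated as late toxicity. This dilutes a descriptive contrast, mostly in the 2-year summary (about 30-34% of the window) and much less over 5 years (about 11-13%). These figures assume six cycles on the nominal schedule; early stopping lowers them and delays raise them. How far the contrast shrinks cannot be stated, because it depends on rates the protocol does not give. The start-of-radiotherapy wording in section 11.2 contradicts section 9.7 and Table 3, but on its own is editorial.

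**What to change.** - In sections 11.2 and 13.5, summarise late radiotherapy toxicity on radiotherapy-related reactions, using the separation in section 10.2, that start after the 3-month boundary. Tabulate chemotherapy-related reactions separately.
- Keep the all-cause table by period. Add one of all reactions starting or still present from the 12-month visit onward, when scheduled PCV has ended. This table does not require a choice between radiotherapy and chemotherapy as the cause.
- For that added table, say which collection rule applies: section 10.2 stops chemotherapy-related reactions 42 days after the last cycle, while the footnotes to Tables 3 and 4 run monitoring to the end of the trial.
- Reconcile the visit timing in section 11.2 with the end-of-radiotherapy schedule in section 9.7 and Table 3.

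The cost is wording and some extra tabulation. No new data are needed, provided the case report forms record the attribution that section 10.2 implies. The small downside is that attribution is unblinded, which is why the all-cause and 12-month tables stay alongside.

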#### Radiological Response rates

Tumour response will be assessed using MRI scans, performed at baseline, 3, 6, 12, 24, 36, 48 and 60 months post-RT, as per standard of care. Response will be evaluated based on the RANO criteria. Additional off-schedule MRI scans may be used in the case of suspected progression.

#### **Progression-free survival (PFS)**

PFS is defined as the time from randomisation to the date of the first documented evidence of progression or death from any cause. Assessment of progression will use response data evaluated by RANO at 3, 6, 12, 24, 36, 48 and 60 months post-RT. Additional unscheduled MRI scans may be used in the case of suspected progression.

#### **Overall survival (OS)**

OS is defined as the time from randomisation to the date of death from any cause. Survival data will be collected at standard follow-up visits.

# 12 Statistical Considerations

# 12.1 Sample size

The required sample size is 246 patients, recruited over 3½ years.

NCF is measured using CTB COMP, calculated from the mean of standardized z-scores for the HVLT-R, TMT-A/B, and COWA. The sample size for NCF at 5 years is based on a two-sample t-test. A Cohen's d of 0.5 is considered a moderate effect size (Cohen 1988); assuming a common standard deviation (SD) of 1 this effect size equates to a mean z-score of 0.5, and is deemed clinically relevant in this setting given that patients are typically young and of working age, so even small deteriorations will likely result in noticeable everyday issues (Giovagnoli and Boiardi 1994; Boele *et al.* 2014). This is the same targeted difference in CTB COMP score adopted in the NRG-BN005 US PBT vs. photon RT glioma study (NCT03180502) (NRG Oncology 2017). Based on a two-sample t-test with 5% two-sided significance and 90% power, 172 patients (86 per arm) are required to detect an effect size of 0.5. Assuming 30% loss to follow-up at 5 years (Cohen 1988; Klein 2019), 123 patients will be required per arm.

## 12.2 Planned recruitment

A total of 246 patients will be recruited from 18-25 UK centres over 3½ years. This provides an approximate recruitment target of 5-6 patients per month.

Based on responses from centre feasibility questionnaires, the estimated potential annual trial recruitment is ~ 85 patients. The numbers selected for the pilot phase allow for lower recruitment rate during year one, and completion of recruitment during the remaining  $2\frac{1}{2}$  years.

# **13 Statistical Analysis**

#### 13.1 General considerations

Statistical analysis for the main trial endpoints is the responsibility of the CTRU Statisticians. The analysis detailed below provides an overview of the analyses to be performed for the main trial. A separate and fully detailed statistical analysis plan (SAP) will be written in accordance with CTRU SOPs, prior to any analyses being performed.

Analysis of the primary and secondary endpoints will be performed on an intention-to-treat (ITT) basis, unless specified otherwise within the SAP.

#### 13.2 Frequency of analysis

A staged assessment approach will be used within the trial with an initial assessment of recruitment and two interim analyses for:

- Evaluating efficacy based on an intermediate endpoint, using all patients' NCF scores at 2 years. Secondary endpoints including treatment compliance and acute and late toxicities up to 2 years will also be assessed.
- Evaluating futility for the primary endpoint when 50% of patients have been followed up for 5-years.

The final primary and secondary endpoint analysis will take place once the final participant has reached their primary endpoint, i.e. 60 months post end of RT treatment, and once all data have been received and cleaned.

# 13.3 Interim analysis

#### Pilot stage – recruitment assessment

After the first 12 months of recruitment, the number of participants recruited and number of centres opened will be explored.

A 50% recruitment rate is assumed in the first 6 months, and a 100% recruitment rate in the following 36 months (3 years). Given that this is equivalent to 39 months at 100% recruitment, the 100% recruitment rate requires 6.3 participants to be recruited per month (246/39 = 6.3). In year 1, this results in a target recruitment rate of 57 patients (50% rate for 6 months and 100% rate for 6 months:  $\frac{1}{2}(6.3^{*}6) + 6.3^{*}6 = 57$ ).

Based on approaches described by Herbert et al (Herbert *et al.* 2019), the following traffic light system will be used to determine the pilot phase outcome.

	Number participants recruited	Number centres	Outcome / action
		open	
Red	< 37 (<64% of year 1 target)	< 9	Full review of feasibility including TSC and EME; potential termination of trial
Amber	37-56 (64-98% of year 1 target)	9 - 11	Assess barriers to recruitment and explore remedial action
Green	57+ (>100% of year 1 target)	12+	Recruitment targets sufficiently high, continue to main phase

The internal pilot stage will be assessed on only the **number of patients recruited** within the first year, centre targets are presented and will be explored for context of remedial action, if required.

#### 2 year early interim efficacy assessment

The first interim analysis will occur after all participants reach 2-year follow-up.

Assessment of efficacy on the intermediate endpoint of 2-year NCF will allow early dissemination and potential practice change if the clinically relevant difference of 0.5 is shown at the 1% level. The study is designed with an intermediate and final primary endpoint, whereby a significant positive treatment effect on either endpoint would warrant change in practice. As such, it is important to preserve the family wise error rate (FWER) in the trial, following the Food and Drug Administration (FDA) guidance on multiple endpoints in clinical trials. The FWER of 0.05 will be preserved using the fall-back method (U.S. Department of Health and Human Services Food and Drug Administration 2017) with alpha of 0.01 allocated to the intermediate, and 0.04 allocated to the final, primary endpoint. Should a significant effect be observed on the intermediate endpoint, the full alpha of 0.05 will be used for the final primary endpoint analysis. Irrespective of early interim assessment outcome, the trial will continue. Assuming the same sample size calculation, using a type I error of 0.04 (5 years) would provide ~89% power. At the 2 year time point, assuming a smaller dropout rate of 10%, a type I error of 0.01 would provide ~87%.

